5.6 Data Analysis

- **Provide sample size determination and analysis (include anticipated rate of screen failures, study discontinuations, lost to follow-up etc.).**

In a recent EPIC study, the minimal clinically important difference for the four EPIC domains was defined as the difference in scores between patients who were completely satisfied with their symptom burden (function and bother combined) versus only somewhat satisfied. Minimally important differences ranged from 0.33 standard deviation (SD) to 0.5 SD, which translated into a difference of six points for urinary incontinence scores, four points for bowel, 10 points for sexual function, and 4 points for hormonal symptoms. In the proposed study, we consider these differences as the clinically meaningful between-group mean difference in symptom reduction. To detect a 0.33 SD difference in symptom reduction between patients receiving the automated PC symptom support versus standard information at 12

month with 90% power, we will need 394 participants (197 per group), based on using a regression analysis adjusting for baseline values (analysis of covariance) with an α of 0.0125 with 0.5 as an assumed correlation between baseline and follow-up symptom scores. Note that the α value was chosen conservatively to detect symptom reduction in any of the four domains. The power will be higher to detect a larger than 0.33 SD between-group difference in symptom reduction and also to detect the same difference with higher correlation than 0.5 between baseline and follow-up symptom values. Assuming conservatively 15% attrition at each assessment time, we propose to enroll 550 participants in total with an anticipated 397 participants to complete assessments at the second assessment time. The number of eligible prostate cancer patients at each site is sufficient for recruitment. For interval scale outcomes measures such as confidence in symptom self-management, the proposed sample size should give adequate power to detect at least 0.33 SD differences between groups.

- **Describe how, where and by whom the data will be analyzed.**

All data will be analyzed at the Ann Arbor VA. The qualitative data analyst, [name], the data manager, [name], and Drs. [name], [name] and [name] will participate in the data analysis.

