Aim 1 initial analyses and data verification: Analyses will be done in three phases. Baseline analysis (data verification) will include examining the distribution of all study variables to assess extreme values, missing data, variances, skewness, and type of distribution. Descriptive statistics will be used to describe the distribution of baseline variables in the two groups. We will use means, medians, and ranges for continuous variables such as age and baseline symptom scores, and we will use proportions for discrete variables. Baseline comparability of the two groups will be assessed using two-group t-tests for continuous variables, and chi-square tests for dichotomous or categorical variables. Variables found to be associated with the study groups will be included in subsequent analyses as covariates to adjust for potential differences between groups, and the results will be interpreted with any baseline imbalances in mind. We also will evaluate bivariate associations between patients' experimental condition and the outcomes, as well as between each covariate and the outcomes and between each covariate and group assignment. These analyses will be done to determine unadjusted measures of effect, assess possible confounders, and anticipate any collinearity in subsequent analyses. We will also report by study group the percent of patients who reached EPIC symptom scores above 70 (i.e., "better symptom burden") at both 5- and 12- months. In the final phase we will use multivariable models to estimate the intervention effect. We will conduct graphical analysis to explore variation in outcome variables over time and between the two experimental groups. We will evaluate the trends in symptom burden, knowledge and information need over time in the two study groups separately. Results of these graphical analyses will be used to fine-tune the analytic course described below.

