Aim 1 outcome analyses: Our primary outcomes for Aim 1 will be changes in symptom burden and bother scores at 5-months relative to baseline, using the EPIC measure. We will also evaluate these outcomes at the 12-month assessment point, but focus on the 5-month for primary outcome assessment as it is closest to the completion of the intervention. Multiple regression analysis will be used to evaluate the primary outcomes. The model will include an indicator for intervention group as the primary independent variable, and treatment type indicator (surgery vs. radiotherapy) and study site indicators as covariates. Baseline variables found to differ between the two study groups in the baseline analysis will also be included as covariates, though we expect the groups to be balanced on demographic and symptom scores by the randomization process. The coefficient for the intervention group indicator will be used to evaluate the impact of the personalized automated prostate cancer symptom management program compared to standard information. For change in symptom burden, we will repeat the analysis using each of the four symptom domains for EPIC. We will use the same analytic approach to evaluate changes in confidence in symptom self-management, our second Aim 1 outcome. We hypothesize that for both Aim 1 outcomes, intervention group survivors will have better scores at both 5- and 12-month assessments relative to those in the group (i.e., less symptom burden and better PC-QOL, more confidence in symptom self-management). For patients with available data at both 5- and 12-months, we will assess the trajectory of symptoms over time. This will be done using a linear mixed-effects model with random effects for each subject, an indicator for intervention group, an indicator of follow-up wave (5 versus 12 months) and an interaction of time by intervention group to model potential changes in the intervention effect on symptoms soon (at 5-months) vs. long (at 12-months) after the intervention is discontinued. If the interaction is not significant, we will drop the interaction term from the model and estimate the time-averaged difference in outcomes between the two study groups. Analyses of other outcomes, such as self-management implementation and confidence, will be done similarly.

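### The primary EPIC regression has no missing-data method, so by default it drops about 83 of 550 men at 5 months and 153 at 12 months, with no check on what that does to the effect

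*Combined protocol and SAP*

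**What the plan says.** All of this is in section 5.6, Data Analysis, unless noted.

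- **Primary outcome:** "Our primary outcomes for Aim 1 will be changes in symptom burden and bother scores at 5-months relative to baseline, using the EPIC measure". The same outcomes are also evaluated at 12 months.
- **Method:** "Multiple regression analysis will be used to evaluate the primary outcomes". The model has an arm indicator, treatment type, site, and any baseline variables found to differ between arms. It gives no analysis set and no rule for men without the follow-up score.
- **Mixed model:** "For patients with available data at both 5- and 12-months, we will assess the trajectory of symptoms over time". A man seen at 5 months and then lost is therefore left out.
- **Missing data:** the one mention in the Aim 1 plan is a descriptive step at data verification, "examining the distribution of all study variables to assess extreme values, missing data, variances, skewness, and type of distribution".
- **Attrition:** "Assuming conservatively 15% attrition at each assessment time", and "we propose to enroll 550 participants in total with an anticipated 397 participants to complete assessments at the second assessment time". The required number is 394, so the expected completers are the number the power calculation rests on.

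The Aim 2 logistic model is said to include every participant; Aim 1 has no such statement. Intention to treat appears only in a title in the reference list (section 9.0).

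**The concern.** The hypothesis is about Veterans assigned to the intervention. A regression on men with follow-up estimates the effect in those who stayed. The two agree only if leavers resemble stayers, given the covariates, in the way that matters for the arm comparison.

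The protocol gives some reason not to take that for granted. Only intervention men receive the monthly automated calls with staff reminders (section 5.5). Under section 5.7, unanswered automated calls lead staff to ask whether the man wishes to continue, and a man who declines is not contacted again. That is a route out of follow-up which the intervention arm meets more often.

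Information is also lost at 12 months. A man seen at 5 months and lost afterwards has a post-intervention EPIC score, yet neither the 12-month regression nor the mixed model uses it.

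**Working it through.** **1. Reproduce the sample size.** Inputs from section 5.6: difference 0.33 SD, 90% power, α 0.0125, baseline to follow-up correlation 0.5, baseline-adjusted analysis. Sidedness is not stated; two-sided is assumed.

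n per arm = 2 × (2.498 + 1.282)² × (1 − 0.5²) / 0.33² = 196.7, so 197 per arm and 394 in total. This matches the plan.

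**2. Reproduce the attrition.**
- 5 months: 550 × 0.85 = 467.5 remain; 82.5 are lost (15%).
- 12 months: 550 × 0.85² = 397.4 remain, matching the stated 397; 152.6 are lost (27.75%).

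The primary time point is 5 months, so 15% bears on it. The 28% bears on the 12-month analysis, which is the time point used for the sample size.

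**3. Effect in stayers against effect in all randomised men.** Assume equal retention r in both arms, a gain of 0.33 SD in stayers, and a fraction f of that gain in leavers.

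Effect in all randomised = 0.33 × [r + (1 − r) × f]. Overstatement = 1 / [r + (1 − r) × f] − 1.

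| Leavers' share of the gain, f | 5 months, r = 0.85 | 12 months, r = 0.7225 |
|---|---|---|
| 1 | 0.330 SD, 0% | 0.330 SD, 0% |
| 0.5 | 0.33 × 0.925 = 0.305 SD, 8% | 0.33 × 0.861 = 0.284 SD, 16% |
| 0 | 0.33 × 0.85 = 0.281 SD, 18% | 0.33 × 0.7225 = 0.238 SD, 38% |

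A simulation of trials of 550 with f = 0 agrees. The follow-up-only estimate averaged 0.333 against 0.282 in all randomised men at 5 months, and 0.328 against 0.236 at 12 months.

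**4. Ignoring the 5-month score at 12 months.** Simulation with 550 men, no true effect, correlation 0.6 between the 5- and 12-month scores (assumed; not in the documents), and about 15% loss between the waves. Loss depends on the 5-month score through a logistic model with slope 0.5 or 1.0 per SD (assumed).
- Dependence in one arm only: complete-case bias of about 0.02 SD at slope 0.5 and 0.05 SD at slope 1.0. A further check of the same mechanism gave about 0.06 SD, so the range is 0.02 to 0.06 SD. It favours the intervention if poorly scoring men leave that arm, and the sign reverses if they leave the control arm.
- Same mechanism with the 5-month score used: bias about 0.
- Same mechanism in both arms: bias about 0 even in the complete-case fit.

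**5. Does imputation correct step 3?** No. With f = 0 at 5 months, imputation by arm from baseline gives 0.33, the same as the complete-case fit, against a true value of about 0.28. Stayers' gains are projected onto leavers.

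**The case against.** The strongest reply is that the plan nowhere prescribes a completers-only analysis. What is documented is silence, and the completers reading is the default that follows from a change score, an ordinary regression and a power calculation resting on 397 completers. That stands, and the point is worded accordingly.

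A reader might go further and infer that the primary result will be 18% or 38% too large. The documents do not support that. Those figures need leavers to gain nothing. Section 5.5 places all four calls within three months, and 5-month survey attempts begin at about month 4, so a man who misses the survey may have had every call and newsletter. Zero gain is less natural still for a man lost between 5 and 12 months. If leavers gain as much as stayers and loss is equal by arm, there is no bias.

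A reader might also infer that loss will be heavier in the intervention arm. The documents give no loss by arm. Both arms complete three surveys and receive an automated EPIC call after each, and repeat contact attempts and mailed paper surveys apply to both (section 5.5). These measures should limit loss, but they are not an analysis rule, and the sample size still allows for 15% at each assessment.

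Finally, the exact imputation model is one of several acceptable choices, and a strict robustness gate would be debatable. Both are accepted in the fix.

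**Conclusion.** The concern holds as a gap in the stated analysis with a conditional consequence. As written, the Aim 1 regressions leave out about 83 men at 5 months and 153 at 12 months. Nothing in the plan tests how the result depends on them, and the 5-month scores of men lost later enter no 12-month comparison of the arms.

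With a 0.33 SD gain in stayers and equal loss by arm, the overstatement is 0% to 18% at 5 months and 0% to 38% at 12 months, depending on what leavers gain. Separately, ignoring the 5-month score costs 0.02 to 0.06 SD at 12 months, but only if loss depends on that score in one arm and not the other. Against a 0.33 SD target, that second bias is small.

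It would be wrong to conclude that imputation alone settles the matter. Under missing at random it recovers the unused 5-month information, but it leaves the case of a programme that helps only stayers uncorrected. Only an analysis that departs from missing at random addresses that case. This should be fixed before outcomes are examined, particularly since the plan lets exploratory graphs adjust the analysis.

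**What to change.** In section 5.6, Aim 1 outcome analyses:

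1. Define the analysis set as all randomised men in their assigned arm.
2. Fit the stated regression after multiple imputation done separately by arm, or use an equivalent likelihood-based model. Use baseline EPIC, site, treatment type and both follow-up waves. Remove the restriction of the mixed model to men with both follow-ups. State that this assumes data missing at random.
3. Pre-specify one control-based sensitivity analysis for each EPIC domain, with missing intervention-arm outcomes imputed from the control arm. Report it beside the primary result and do not use it as a pass/fail gate.
4. Report loss of EPIC data by arm at each wave.

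**Cost.** Wording and modest programming; recruitment and contact procedures do not change. The sensitivity estimate may be smaller and have less power. If leavers gain nothing, then even counting all 550 outcomes as observed, power is about 90% for 0.281 SD at 5 months and 77% for 0.238 SD at 12 months, where 377 per arm would be needed for 90%. This is why it should inform interpretation and not act as a gate.

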5.2 Recruitment Methods

- **State how many subjects will be needed.**

Veteran participants:

We estimate as many as 553 - 650 veterans will be randomized.

VA employees:

We plan to interview up to 40 key stakeholders (up to 4 PCPs and 4 specialists at each site, plus interviews of stakeholders at the VISN and national level), recruited and interviewed by AAVA project staff.

- **Describe when, where, how and by whom potential subjects will be identified and recruited.**

RCT:

Recruitment and informed consent. We have been granted a waiver of documentation of informed consent and HIPAA Authorization. Potential participants will be sent an introductory letter and a patient information sheet. The introductory letter will briefly describe the study and include a local or toll free number to call if the patient is not interested in participating or would like more information. After one week, a study coordinator will telephone those Veterans who did not opt-out, and if the patient is interested, the coordinator will ensure the patient is properly informed, obtain verbal informed consent, administer the Brief Screener by phone and determine whether that Veteran meets the criteria of having a clinically meaningful symptom burden score (1 or higher on any one symptom, as a measure of low function or high symptom burden) on at least one item.

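### The sample size assumes adjustment for baseline EPIC, but the Aim 1 model does not list it: at r = 0.5 and 550 enrolled, power is about 86% at 5 months and 78% at 12 months, against 95% and 90% with adjustment

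*Combined protocol and SAP*

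**What the plan says.** All of the text is in section 5.6, Data Analysis.

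- **Sample size paragraph.** The target is set out as "To detect a 0.33 SD difference in symptom reduction between patients receiving the automated PC symptom support versus standard information" at 12 months with 90% power. The 394 participants (197 per group) are "based on using a regression analysis adjusting for baseline values (analysis of covariance) with an α of 0.0125", with an assumed correlation of 0.5 between baseline and follow-up scores. Enrolment is 550, with 15% attrition at each assessment and 397 expected at the second follow-up.
- **Aim 1 outcome analyses.** The primary outcome is change in EPIC from baseline, with a "focus on the 5-month for primary outcome assessment as it is closest to the completion of the intervention". On covariates: "The model will include an indicator for intervention group as the primary independent variable, and treatment type indicator (surgery vs. radiotherapy) and study site indicators". The paragraph continues: "Baseline variables found to differ between the two study groups in the baseline analysis will also be included as covariates". The same sentence says the groups are expected to be balanced on symptom scores.
- **Aim 1 initial analyses and data verification.** The conditional rule appears here too: "Variables found to be associated with the study groups will be included in subsequent analyses as covariates to adjust for potential differences between groups". No threshold for an association is given.
- **Trajectory analysis.** This is a "linear mixed-effects model with random effects for each subject, an indicator for intervention group, an indicator of follow-up wave (5 versus 12 months") and their interaction. It lists no baseline score.

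The Aim 2 analysis does name the baseline EPIC score as an independent variable. Section 5.2 gives a larger enrolment figure: "We estimate as many as 553 - 650 veterans will be randomized".

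**The concern.** The sample size and the analysis describe two different models for the same outcome. An analyst following the sample size paragraph would adjust for baseline EPIC. One following the outcome paragraph would not, unless a baseline test happened to flag it.

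Both models estimate the arm difference without bias in a randomized trial, so validity is not at risk. What is at stake is precision: the 90% power depends on the variance reduction from baseline adjustment, and the listed model gives that up. A second consequence is that the content of the primary model, for each of four EPIC domains, would depend on the result of a baseline test whose threshold is not stated.

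**Working it through.** **Inputs from section 5.6.** Difference d = 0.33 SD; alpha = 0.0125; power 90%; r = 0.5; 550 enrolled; 15% attrition per assessment.

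**Assumptions added.**
- The test is two-sided (a one-sided test would give 342, not 394).
- The SD is the same at baseline and follow-up.
- Alpha 0.0125 carries over to 5 months, because the outcome paragraph gives none.
- Site and treatment type explain no variance.

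**1. Reproduce the plan's figure.** n per arm = 2(z₀.₉₉₃₇₅ + z₀.₉₀)² V / d², with z-values 2.498 and 1.282, so (2.498 + 1.282)² = 14.28.
- ANCOVA, V = 1 − r² = 0.75: 2 × 14.28 × 0.75 / 0.1089 = 196.7, that is 197 per arm and 394 in total. This matches the plan exactly.
- Change score without baseline, V = 2(1 − r) = 1.0: 2 × 14.28 × 1.0 / 0.1089 = 262.3 per arm, about 525 in total.

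The plan's figure therefore depends on baseline adjustment. The variance without it is one third larger (1.0 / 0.75 = 1.33).

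**2. Power at the planned enrolment.** Power = Φ(d / √(2V/n) − 2.498), with n per arm. Completers are 550 × 0.85 = 467 at 5 months and 550 × 0.85² = 397 at 12 months.

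| Time point | Completers | Change score, no baseline | With baseline |
|---|---|---|---|
| 5 months (primary) | 467 | 85.7% | 94.7% |
| 12 months, expected | 397 | 78.5% | 90.3% |
| 12 months, stated requirement | 394 | 78.2% | 90.0% |

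Using the noncentral t distribution, the 467 and 397 rows become 85.5% against 94.6% and 78.1% against 90.0%.

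**3. Enrolment needed for 90% without baseline.** 525 / 0.85 = 618 for 5 months, inside the 553–650 of section 5.2. 525 / 0.85² = 727 for 12 months, above it. Across 553–650 randomized, the listed model gives 86–92% at 5 months and 79–86% at 12 months.

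**4. Dependence on r** (no baseline against baseline).

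| r | 467 completers | 394 completers |
|---|---|---|
| 0.3 | 69.7% vs 89.3% | 60.7% vs 82.5% |
| 0.5 | 85.7% vs 94.7% | 78.2% vs 90.0% |
| 0.7 | 98.2% vs 99.4% | 95.8% vs 98.2% |

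The unadjusted model reaches 90% at r of about 0.55 (467 completers) or 0.62 (394).

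**5. What the conditional rule recovers.** 20,000 trials were simulated per size at r = 0.5, with four sites and a two-level treatment indicator in every model. Baseline was added only if its two-group t-test fell below an assumed threshold.

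| Completers | Never adjust | p<0.05 | p<0.10 | p<0.20 | Always adjust |
|---|---|---|---|---|---|
| 466 | 84.7% | 85.9% | 86.7% | 88.2% | 94.4% |
| 394 | 77.6% | 78.8% | 79.6% | 81.1% | 89.5% |

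The rule gains 1.2 to 3.5 points, out of a gap of 9.7 points (466) or 11.9 points (394). Under the null at 466 completers, rejection was 1.3% for both fixed models and 0.8–1.0% for the conditional rule, against a nominal 1.25%.

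**The case against.** The outcome paragraph says what the model will include, not that it includes nothing else. Its lists are not clearly exhaustive, since the mixed model omits site and treatment type, which the main model carries. The sample size paragraph does name ANCOVA, so the multiple regression might be that same ANCOVA, incompletely described. This reading is possible but strained: the outcome paragraph mentions symptom scores only within the conditional rule, as something expected not to need adjustment. At best the text supports both readings.

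The power loss can also be called modest where it matters most. The plan promises 90% only at 12 months and makes no power statement for 5 months. At 5 months and 550 enrolled, the shortfall from 90% is about 4 points, and it disappears near the top of the 553–650 range or at r of about 0.55. That is fair. But the 12-month comparison is the one the plan does power, and there the listed model stays below 90% across the whole enrolment range at r = 0.5.

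Finally, the figures rest on equal SDs. At r = 0.5 and 467 completers, a baseline SD of 0.8, 0.9, 1.1 or 1.2 times the follow-up SD gives change-score power of 91.8%, 89.3%, 81.2% or 75.9%. So 86% is a central value that could move either way. All four values remain below the 94.7% with adjustment, which does not depend on this ratio.

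**Conclusion.** The concern holds. The stated 90% power comes from a model with baseline EPIC as a covariate, and the analysis text does not specify that model. Under the plan's own assumptions and 550 enrolled, the listed model gives about 86% at 5 months and about 78% at 12 months, where the plan states 90%. The conditional rule closes only a small part of the gap at the thresholds tried.

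The size of the loss depends on r, on equal SDs at baseline and follow-up, and on alpha 0.0125 applying at 5 months. Baseline adjustment gave the higher power at every value examined. There is no bias and no inflation of type I error. The plan should be corrected because its two statements conflict and the remedy is simple.

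**What to change.** In section 5.6, *Aim 1 outcome analyses*, state that the model for each EPIC domain always includes that domain's baseline EPIC score, together with arm, site and treatment type, whatever the baseline comparison shows. State that the mixed model includes the baseline score too. The response can stay as change from baseline, because with baseline as a covariate the arm coefficient is identical to that from ANCOVA on the follow-up score. Exempt baseline EPIC from the found-to-differ rule both there and in *Aim 1 initial analyses and data verification*.

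If the change-score model without baseline is kept on purpose, restate the power in the sample size paragraph as about 86% at 5 months and 78% at 12 months (550 enrolled, r = 0.5).

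The cost is one sentence and a short exemption. Baseline EPIC is already collected, so no participants or procedures are added.

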There are three primary Veteran-reported trial outcomes which will be measured at 5- and 12-months post enrollment: 1) confidence in symptom self-management, 2) implementation of symptom self-management, and 3) symptom burden and PC-QOL. Self-efficacy in patient-physician interactions will also be assessed at baseline, 5-months and 12-months. Participants in the trial will be randomized by computer by VA Ann Arbor Healthcare System (VAAHS) study staff. We hypothesize better outcomes in the intervention arm relative to enhanced usual care. The impact of the intervention on two secondary psychosocial outcomes, overall subjective health and perceptions of cancer control, will be assessed only at the 12-month time point, when we believe the intervention is most likely to have had its impact on these outcomes. The trial will be conducted in four VA sites (Ann Arbor, Cleveland, Pittsburgh, and St. Louis) with a large and racial/ethnically diverse population of PC survivors between 1-10 years post-treatment. The intervention is based on a conceptual framework that describes how self-management contributes to positive outcomes for cancer patients and survivors; we also will utilize theoretical constructs from patient empowerment and cognitive behavioral therapy (CBT) to inform the content of our intervention. We will compare the quality of health care received in intervention and control subjects using guidelines for prostate cancer survivorship care developed by the Michigan Cancer Consortium as a benchmark. Finally, we will prepare for implementation of the intervention on a broader scale through a formative evaluation. This design will allow us to understand how the intervention can best optimize the quality of life and quality of care for Veterans with PC, and will inform how to implement the program more broadly with our primary care partners.

- **Include a description of how anticipated risk will be minimized and include an analysis of risk vs. potential benefit.**

How anticipated risk will be minimized:

Veteran participants:

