We will use the Expanded Prostate Cancer Index (EPIC) to assess PC-symptom burden and associated PC-QOL at the baseline, 5- and 12-month assessments. The EPIC was developed by our study consultant, [name], and has been widely used in prostate cancer survivorship research. The EPIC is a 26-item measure that assesses symptom burden in four domains: urinary symptoms (9 items), bowel symptoms (6 items), sexual symptoms (6 items) and vitality (5 items). Each domain has a subscale related to function and bother which together contribute to disease specific quality of life. Prior work by [name] and colleagues has shown that these domains have good internal consistency (Chronbach's alpha > 0.82 for each domain) and correlate highly with other established measures of QOL.¹⁰⁷ Each domain has a range of possible scores from 0 to 100, with lower scores indicating worse symptom burden. Lower EPIC scores for any one domain are associated with lower function in that domain (e.g., lower sexual health function) and lower QOL. Thus higher symptom burden, which reflects both function and bother scores, translate into lower EPIC scores. Based on consultation with [name] and on prior work by his team, for purposes of this study we will consider a score of 70 or less to indicate "clinically meaningful symptom burden" for any one domain. We will conduct primary outcome analyses using the EPIC. Self-efficacy in patient-physician interactions will also be assessed both at baseline and 12-months using a 5-item short form version of the Perceived Efficacy in Patient-Physician Interactions (PEPPI). The PEPPI was developed to measure older patients' self-efficacy in obtaining medical information and attention to their medical concerns from physicians. PEPPI has good convergent and discriminant validity and strong reliability ($\alpha=0.93$).

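### The Aim 1 outcome model does not carry over the baseline EPIC adjustment on which the 90% power rests, and sections 5.1 and 5.6 differ on which outcomes are primary

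*Combined protocol and SAP*

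**What the plan says.** **Sample size (section 5.6).** The 394 participants (197 per group) for 90% power at 12 months are "based on using a regression analysis adjusting for baseline values (analysis of covariance"), with a 0.33 SD difference, alpha 0.0125 and a baseline to follow-up correlation of 0.5. On the alpha it adds: "Note that the α value was chosen conservatively to detect symptom reduction in any of the four domains". With 15% attrition at each assessment, 550 enrolled leave 397. Sections 5.1, 5.2 and 5.4 expect 553 to 650 randomized.

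**Outcome model (section 5.6, Aim 1 outcome analyses).** The text opens by naming the endpoint: "Our primary outcomes for Aim 1 will be changes in symptom burden and bother scores at 5-months relative to baseline, using the EPIC measure". Twelve months is also evaluated, but 5 months is the focus. The regression holds the group indicator, then a "treatment type indicator (surgery vs. radiotherapy) and study site indicators as covariates". For anything else: "Baseline variables found to differ between the two study groups in the baseline analysis will also be included as covariates". The same sentence expects randomization to balance the groups on symptom scores.

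**Primary status.** Section 5.1: "There are three primary Veteran-reported trial outcomes which will be measured at 5- and 12-months post enrollment", namely confidence in self-management, implementation of self-management, and symptom burden with prostate cancer quality of life. Section 5.5: "We will conduct primary outcome analyses using the EPIC". The Aim 1 analysis calls confidence the second Aim 1 outcome, and later groups it with implementation under other outcomes.

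**The concern.** Subtracting the baseline score is not the same as adjusting for it. At a correlation of 0.5, a change score has a third more residual variance than an analysis of covariance (1.0 against 0.75). An analyst who follows the Aim 1 model text would fit the less precise model, while the report would cite a power figure that belongs to the more precise one.

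The second issue is smaller. If section 5.1 stands, confidence and implementation are primary but have no share of alpha. If the Aim 1 analysis stands, they are not primary. With both texts in force, the choice of what to headline could be made after the results are known.

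**Working it through.** **Inputs.** All from section 5.6 unless noted: difference d = 0.33 SD, alpha 0.0125, r = 0.5, 1:1 allocation, 550 enrolled, 15% attrition per assessment. The range 553 to 650 is from sections 5.1, 5.2 and 5.4. My assumptions: equal SD at baseline and follow-up, the same effect and r at both times, and no variance explained by treatment type or site (the plan gives no figure).

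**Residual variance V, in SD² units.** With the baseline score as covariate, V = 1 − r² = 0.75. Change score without it, V = 2(1 − r) = 1.0.

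**Reproducing the plan's figure.** n per arm = 2V(z_alpha + z_beta)²/d², with z_alpha = 2.4977 (two-sided 0.0125) and z_beta = 1.2816.
- V = 0.75: 2 × 0.75 × (3.7793)²/0.1089 = 196.7, so 197 per arm and 394 in total. This matches. A one-sided test gives 171 per arm, which does not.
- V = 1.0: 262.3, so 263 per arm and 526 in total.
- Completers: 550 × 0.85 = 467.5 at 5 months; 550 × 0.85² = 397.4 at 12 months, matching the stated 397.

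**Power** = Φ(d/√(2V/n) − 2.4977), n per arm. For example, at 5 months with 550 enrolled, n = 233.75: 0.33/√(2/233.75) = 3.568, less 2.498 = 1.070, giving 85.8%.

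| Time | Enrolled | Completers | Without baseline score | With baseline score |
|---|---|---|---|---|
| 5 months | 550 | 467.5 | 85.8% | 94.8% |
| 5 months | 553 | 470.1 | 86.0% | 94.9% |
| 5 months | 650 | 552.5 | 91.6% | 97.6% |
| 12 months | 550 | 397.4 | 78.6% | 90.3% |
| 12 months | 553 | 399.5 | 78.8% | 90.5% |
| 12 months | 650 | 469.6 | 85.9% | 94.9% |

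**Sensitivity to r (550 enrolled).** For r from 0.4 to 0.6, the 5-month change score gives 77.6% to 93.2%, against 91.8% to 97.5% with the baseline score. At 12 months the ranges are 69.3% to 88.1% and 86.2% to 94.7%. The 5-month change score passes 90% from r of about 0.56.

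**Does the conditional rule recover the loss?** The plan gives no threshold for a difference between groups; I assume p < 0.05. In 20,000 simulated trials at 197 per arm and r = 0.5, the baseline score entered in about 5% of trials. Power was 79.0%, against 77.9% if it never enters and 89.3% if it always does.

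**Alpha.** Four EPIC domains at 0.0125 use 4 × 0.0125 = 0.05, which leaves nothing for confidence or implementation.

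**The case against.** The strongest reply is that section 5.6 does specify baseline adjustment, in its sample size paragraph, and that the Aim 1 covariate list does not claim to be complete. The first half is true. But the Aim 1 text is where the model is defined. It gives its own list, and its remark that symptom scores should be balanced places them under the conditional rule. The two paragraphs should not have to be combined by inference.

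A reader might infer that the trial simply falls below 90% power at its primary analysis. The documents do not support that without conditions. The 90% is stated for 12 months, not 5. At 650 randomized the 5-month change score has 91.6%, and at 550 it reaches 90% once r is about 0.56. The plan also puts the minimally important difference at 0.33 to 0.5 SD; at 0.5 SD and r = 0.5 the change score has over 99% power at either time. What remains is that the trial was sized on 0.33 SD and r = 0.5, and at 12 months the unadjusted model stays below 90% across the whole planned enrolment range.

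Two other strong readings also fail. Section 5.5 does not reserve primary status for the EPIC: its sentence sits in a description of the instrument and excludes nothing. The conflict is between section 5.1 and the Aim 1 analysis, which is itself mixed on confidence; the sample size paragraph also comments on power for confidence. Nor does the mention of bother scores establish eight primary tests. Section 5.5 says "Each domain has a subscale related to function and bother which together contribute to disease specific quality of life", the sample size paragraph treats function and bother as combined, and the Aim 1 analysis is repeated over four domains.

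**Conclusion.** The point holds as an inconsistency between the model that sized the trial and the model written for its analysis. On the plan's own assumptions, leaving out the baseline score costs 9.0 percentage points of power at 5 months (94.8% to 85.8%) and 11.7 at 12 months (90.3% to 78.6%) with 550 enrolled. The cost shrinks with higher enrolment or higher correlation. These figures rest on equal variances, a common effect and correlation at both times, and no contribution from treatment type or site. The sample size of 394 is correct for the model it assumes. The change-score estimate is unbiased under randomization, so validity is not in question.

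The conflict over primary outcomes is a secondary point of wording, but it needs settling before the data are analysed.

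**What to change.** 1. In the Aim 1 outcome analyses of section 5.6, name the baseline EPIC domain score as a prespecified covariate in each domain model, whether or not the groups differ on it. In the sample size paragraph, state that the 90% at 12 months depends on that term.
2. Reconcile section 5.1 with the Aim 1 analysis in one of two ways. Either the four EPIC domain scores at 5 months are the only primary outcomes, each tested at two-sided 0.0125 or by Holm across the four, and confidence, implementation and the 12-month results are secondary. Or every outcome kept as primary, implementation included, enters the alpha split. For example, four domains plus confidence and implementation at 5 months would be six tests at 0.05/6 = 0.0083. The choice is the sponsor's. Any power quoted for non-EPIC outcomes should be marked as an assumption, because the plan gives a correlation only for symptom scores.
3. Add one sentence saying that function and bother are combined within each domain score.

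The cost is one model term, using a score already collected at baseline, and a few sentences. The first option in item 2 leaves fewer outcomes that can be called primary; the second lowers the alpha for each EPIC test.
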